#### 7.6.4.1 Hematology

- Absolute neutrophil count (ANC) (Decrease)
- Hemoglobin (Hgb) (Both directions)
- Hematocrit (HCT) (Both directions)
- Platelet count (Decrease)
- White blood cell (WBC) count (Both directions)
- Lymphocyte count (Both directions)

#### 7.6.4.2 Chemistry

- AST (Increase)
- ALT (Increase)
- Alkaline phosphatase (ALP) (Increase)
- Albumin (Both)
- Total Bilirubin (TBL) (Increase)
- Creatinine (Increase)
- Blood urea nitrogen (BUN) (Both directions)
- Calcium (absolute, albumin-corrected) (Both directions)
- Gamma-glutamyl transferase (GGT) (Increase)
- Sodium (Both directions)
- Potassium (Both directions)
- Chloride (Both directions)
- Lactate dehydrogenase (LDH) (Increase)
- Lipase (Increase)
- Amylase (Increase)
- Magnesium (Decrease)

A table presenting number and percentage of patients with post-baseline CTC grade increased from baseline (any grade, grade 3-4) will be generated for the above selected laboratory parameters. If lab parameters do not have toxicity grade in CTCAE v5.0, it will not be presented in the table. In addition, a table presenting hepatic impairment evaluation and a table presenting renal impairment evaluation will be generated. The hepatic and renal impairment evaluation criteria can be found below:

- Hepatic impairment evaluation

Normal:  $TBL \leq ULN$  and  $AST \leq ULN$

Mild:  $ULN < TBL \leq 1.5 \times ULN$  or  $AST > ULN$

Moderate:  $1.5 \times ULN < TBL \leq 3 \times ULN$

Severe:  $TBL > 3 \times ULN$

- Renal impairment evaluation based on baseline estimated glomerular filtration rate (eGFR, mL/min/1.73 m^2) (Levey et al., 2009)

Normal:  $eGFR \geq 90$  mL/min/1.73 m^2

Mild: eGFR between 60 to 89 mL/min/1.73 m^2 (inclusive)

Moderate: eGFR between 30 and 59 mL/min/1.73 m^2 (inclusive)

Severe:  $eGFR < 30$  mL/min/1.73 m^2

- Where  $eGFR = 141 \times \min(Scr/\kappa, 1)^\alpha \times \max(Scr/\kappa, 1)^{-1.209} \times 0.993^{\text{Age}} \times 1.018$  [if female]  $\times 1.159$  [if black]
  - Scr is serum creatinine in mg/dL,
  - $\kappa$  is 0.7 for females and 0.9 for males,
  - $\alpha$  is -0.329 for females and -0.411 for males
  - min indicates the minimum of Scr/ $\kappa$  or 1
  - max indicates the maximum of Scr/ $\kappa$  or 1
  - age = years
- Renal impairment evaluation based on Cockcroft and Gault equation (calculated creatinine clearance)

Severe:  $calCrCL < 30$

Moderate:  $30 \leq calCrCL \leq 59$

Mild/Normal:  $calCrCL \geq 60$

Where  $\text{calCrCl}(\text{male}) = ([140-\text{age}] \times \text{weight in kg}) / (\text{serum creatinine in mg/dL} \times 72)$ ;  
 $\text{calCrCl}(\text{female}) = \text{calCrCl}(\text{male}) \times 0.85$

A listing of patients who met Hy's Law criteria will be provided. Hy's Law criteria are defined as follows:

- ALT  $\geq 3 \times \text{ULN}$  or AST  $\geq 3 \times \text{ULN}$
- Total bilirubin TBL  $\geq 2 \times \text{ULN}$
- ALP  $\leq 2 \times \text{ULN}$  or missing

## 7.6.5 Additional Safety Analyses

### 7.6.5.1 Vital Signs

Vital signs visits will be included in listings. Vital sign abnormality will be summarized by maximum and minimum post-baseline value. Abnormal values are defined as an absolute value outside the defined range in Table 5.

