Statistical Methods:	Safety: Safety assessments will include AEs, including incidence of SAEs, clinical laboratory tests, vital signs, physical examinations, cardiac function tests, and ECGs. The incidence of DLTs will be evaluated for each dose level. All treatment-emergent adverse events (TEAEs) will be summarized by system organ class and preferred term for each dose level or cohort in the dose escalation and dose expansion phases of the study separately. All TEAEs will be summarized by incidence, severity, and relationship to study drug(s). Clinical laboratory tests and vital signs will be summarized descriptively for each dose level in the dose escalation phase and separately for the dose expansion phase of the study. All abnormal findings in clinical laboratory test results, vital signs, physical examination, cardiac function tests, and ECGs will be listed. Efficacy: Objective response rate, CBR, and each BOR category will be calculated along with the 95% confidence intervals (CIs) based on the exact method. The Kaplan-Meier method will be used for the analyses of PFS, OS, and DOR. Time to response will be summarized among responders.

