## **9.0 STATISTICAL METHODS PLANNED IN THE PROTOCOL AND DETERMINATION OF SAMPLE SIZE**

### **9.1 General Considerations**

In general, continuous data will be summarized by descriptive statistics, including number of patients, mean, standard deviation, median, minimum, and maximum. Categorical data will be summarized by the number and percentage of patients.

A description of analysis methods and detailed definitions for efficacy and safety endpoints will be provided in the statistical analysis plan (SAP). The potential impact of COVID-19 on this trial will be assessed. Any changes to the analyses that are required due to COVID-19 will be detailed in the SAP.

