## 9.6 Planned Analyses

### 9.6.1 Safety

Safety assessments will include Safety Population with treatment-emergent AEs with categorization of treatment related with incidences of serious and severe ( $\geq$  Grade 3) AEs, clinical laboratory tests including cardiac function tests, vital signs, physical examinations, and ECGs.

Adverse events and toxicity severity will be evaluated according to NCI-CTCAE Version 5.0 toxicity grading system. Safety assessments will be performed by medical review of AEs, vital signs, and laboratory results.

The incidence rate of DLTs will be evaluated by dose level for the DLT Population. Treatment-emergent AEs will be summarized by preferred term, system organ class, NCI-CTCAE grade of severity, and relationship to the study treatment by dose level for Phase 1b (Dose Escalation), CCI [REDACTED] for the Safety Population. All TEAEs will be summarized by incidence, severity, and relationship to study drug(s).

A TEAE is defined as (regardless of intensity), any AE that occurs after initiation of study treatment on C1D1 until 60 days (inclusive) after the last dose of study treatment. Adverse events with a starting date after the start of new anti-cancer therapy are not considered TEAEs.

Vital signs (including change in weight) and clinical laboratory test results will be summarized descriptively by dose level in Phase 1b (Dose Escalation) CCI [REDACTED] [REDACTED] for the Safety Population. A listing and summary of patients who discontinued study drug(s) due to an AE will be provided.

A data listing for deaths will be provided.

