**Table 6: ECG Outlier Criteria**

ECG Interval	Categorical Outlier Criteria
QTcF	Male: Treatment-emergent value of > 450 and $\leq$ 480 ms when not present at baseline (new onset)
	Male: Treatment-emergent value of > 480 and $\leq$ 500 ms when not present at baseline (new onset)
	Male: Treatment-emergent value of > 500 ms when not present at baseline (new onset)
	Increase of QTc from baseline of > 30 and $\leq$ 60 ms
	Increase of QTc from baseline > 60 ms
	Female: Treatment-emergent value of > 470 and $\leq$ 480 ms when not present at baseline (new onset)
	Female: Treatment-emergent value of > 480 and $\leq$ 500 ms when not present at baseline (new onset)
	Female: Treatment-emergent value of > 500 ms when not present at baseline (new onset)
	Increase of QTc from baseline of > 30 and $\leq$ 60 ms
	Increase of QTc from baseline > 60 ms
PR	Increase of PR from baseline > 25% resulting in PR > 200 ms
QRS	Increase of QRS from baseline > 25% resulting in QRS > 120 ms
HR	Decrease of HR from baseline > 25% resulting in HR < 50 bpm
	Increase of HR from baseline > 25% resulting in HR > 100 bpm

Number and percentages of categorical outliers will be summarized for each treatment group. A patient will be counted only once for a particular outlier event if the patient experiences more than 1 episode of that event.

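### The SAP names no by-dose descriptive tables for vital signs, weight change or laboratory values, although the protocol promises them, and its vital-sign flags have no baseline condition

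*SAP*

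**What the plan says.** **Protocol.** Section 9.6.1 states: "Vital signs (including change in weight) and clinical laboratory test results will be summarized descriptively by dose level in Phase 1b (Dose Escalation". The Statistical Methods part of the synopsis repeats this without weight: "Clinical laboratory tests and vital signs will be summarized descriptively for each dose level in the dose escalation phase". Section 9.1 says what descriptive means for measurements: "continuous data will be summarized by descriptive statistics, including number of patients, mean, standard deviation, median, minimum, and maximum".

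**SAP, vital signs (7.6.5.1 and Table 5).** There are two outputs. The first is "Vital signs visits will be included in listings". The second is an abnormality summary based on each patient's highest and lowest post-baseline value, where "Abnormal values are defined as an absolute value outside the defined range in Table 5". Table 5 gives high and low limits for blood pressure, heart rate, temperature and respiratory rate. Weight is not in it.

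**SAP, laboratory (7.6.4).** "A table presenting number and percentage of patients with post-baseline CTC grade increased from baseline (any grade, grade 3-4) will be generated", and "If lab parameters do not have toxicity grade in CTCAE v5.0, it will not be presented in the table". There are also hepatic and renal impairment tables and a Hy's Law listing.

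**SAP, ECG (7.6.5.2 and Table 6).** Numeric parameters are summarized at baseline, at their worst post-baseline value and as worst change from baseline. The QTcF value categories require new onset, for example "Male: Treatment-emergent value of > 500 ms when not present at baseline (new onset".

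**The concern.** Safety and tolerability is the primary Phase 1b objective, and dose levels may hold as few as 3 patients. In groups that small, a table of values and changes by dose level shows a shift in blood pressure, weight or a laboratory value more directly than a count of patients who cross a limit. A programmer who follows SAP 7.6 as written produces only the counts and the listings.

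Blood pressure is a signal the plan itself treats as relevant. Hypotension is a named category of other safety observations in SAP 7.6.2, and Protocol 5.10.3 addresses antihypertensive drugs around each NKTR-255 dose. With no baseline condition, the vital-sign counts also mix abnormalities that were there before NKTR-255 with those that arose afterwards.

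**Working it through.** The plan gives no figure on this point, so there is nothing to reproduce. The check compares the texts and then applies Table 5 to the documents' own limits.

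**1. Promise against named output**

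| Data | Protocol 9.6.1 with 9.1 | Output named in SAP 7.6 | Not named |
|---|---|---|---|
| Vital signs | n, mean, SD, median, min, max by dose level | Listing; abnormality summary against Table 5 | Descriptive summary of values |
| Weight change | Same | None; weight appears in SAP 7.3.1 as a baseline characteristic | Any post-baseline summary, although Protocol 7.13 has weight recorded on Day 1 of each cycle |
| Laboratory values | Same | CTC grade increase (any grade, grades 3-4); hepatic and renal categories; Hy's Law listing | Descriptive summary of values; any place in the grade table for parameters without a CTCAE grade |

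The laboratory counts are relative to baseline grade, so the missing baseline condition concerns vital signs only. A laboratory shift within one grade is still not summarized. The eGFR-based renal table uses baseline eGFR and so shows no on-treatment change. SAP 7.6 keeps the planned summaries by dose group.

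**2. Do the general sections fill the gap?** SAP 6.1 says how continuous variables are summarized, and SAP 6.6.1 defines change from baseline. No vital-sign, weight or laboratory output in SAP 7.6 calls on either. The ECG subsection, by contrast, names its numeric and change summaries. The visible items in SAP 12.0 do not mention vital signs, weight or laboratory tables.

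**3. Table 5 applied to the documents' own limits.** Exclusion criterion 24 requires screening pressure below 150 systolic and 90 diastolic. Table 5 flags systolic below 90, diastolic below 60, and heart rate below 60 or above 100. With whole-number readings:

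- Systolic 149 to 90: a fall of 149 − 90 = 59 mmHg, no systolic flag.
- Diastolic 89 to 60: a fall of 89 − 60 = 29 mmHg, no diastolic flag.
- Heart rate 60 to 100: a rise of 40 bpm, no flag.
- Heart rate 58 before and after treatment: 58 < 60, so flagged with a change of 0.

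**4. Illustration with assumed values.** Take one normally distributed systolic reading per patient with baseline mean m and standard deviation SD, and a uniform fall of 20 mmHg. The documents give none of these values. Group sizes are 3 (the minimum per dose level) and 6 (the minimum to define the RP2D).

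- Per patient: p = Φ((90 − (m − 20))/SD). At least one flag among n patients: 1 − (1 − p)^n.
- m = 130, SD = 15: p = Φ(−20/15) = 0.091. For n = 3, 1 − 0.909³ = 25%. For n = 6, 1 − 0.909⁶ = 44%.
- m = 140, SD = 10: p = Φ(−3) = 0.1%, giving 0.4% (n = 3) and 0.8% (n = 6).
- m = 120, SD = 15: p = Φ(−10/15) = 25%, giving 58% (n = 3) and 83% (n = 6).

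These three cases span the range for m of 120 to 140 and SD of 10 to 15. In the middle case a group of 6 shows no flag at all with probability 56%. The SAP uses the lowest of many readings, and the diastolic row adds further chances of a flag, so real rates would be higher. The figures show only that a real shift can leave the count at zero.

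**The case against.** **The SAP does not say the descriptive tables are dropped.** A reader might infer that the SAP replaces them. The documents do not go that far: SAP 6.1 has a default of presentation by dose level and conventions for continuous variables, and one item in SAP 12.0 is redacted. This stands. The supportable statement is that the tables are not named, that the sections which list the outputs name others, and that no visible item declares a departure.

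**The protocol promises less than a reader might infer.** It promises descriptive summaries by dose level and names change only for weight. It does not promise change from baseline by visit, worst post-baseline change or new-onset flags, and Protocol 9.1 leaves detailed safety definitions to the SAP. This stands too. Those additions are improvements and do not repair a broken commitment.

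**A falling blood pressure would not necessarily go unseen.** Hypotension adverse events are tabulated by grade, seriousness and relationship to NKTR-255. Table 6 flags heart-rate changes above 25% that end below 50 or above 100 bpm. Vital signs are listed, which is readable for about 30 patients. These safeguards are real but partial. Under Protocol 7.1 a vital-sign abnormality becomes an adverse event only if the investigator judges it clinically significant. The ECG section covers heart rate but not blood pressure, and a listing is not a summary by dose.

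**Lost power cannot be claimed.** A reader might want to express the gap as power against a dose trend. The plan contains no trend test, and the answer turns on the assumed mean fall at the lowest dose. One illustration assumed 30 patients in 5 levels of 6, baseline systolic mean 128, SD 13, capped at 150, change SD 12, and 5 mmHg more fall per level. Power for counts below 90 mmHg ran from about 14% with no fall at the lowest dose to 40% with a 20 mmHg fall there, against about 85% for change from baseline. Adding the diastolic row under further assumptions raised the 14% to 30%. The direction favours change from baseline, but the point does not rest on any of these figures.

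**Conclusion.** The point holds as a mismatch between the protocol's promise and the outputs the SAP names. Three sets of promised by-dose summaries (vital signs, weight change and laboratory values) have no named table, and weight has no post-baseline output at all. Table 5, followed literally, counts unchanged pre-existing values as abnormal and leaves falls of up to 59 mmHg systolic and 29 mmHg diastolic unflagged for a patient entering at the screening limit.

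The weight of the point is moderate. The analyses are descriptive, and nothing visible ties Table 5 to dose decisions, which rest on DLTs, the Bayesian model and clinical review. The conclusion assumes that the redacted item in SAP 12.0 and other redacted text do not name these tables. The percentages in step 4 of the working depend on assumed blood pressure distributions and are illustrative only.

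**What to change.** - In SAP 7.6.4 and 7.6.5.1, name the protocol's descriptive summaries by dose level for vital signs, weight change and every listed laboratory parameter, including those without a CTCAE grade. If any are to be left out, say so and give the reason in SAP 12.0.
- As an improvement beyond the protocol's promise, add change from baseline and worst post-baseline change for the same data, as the ECG subsection already does, using the definition in SAP 6.6.1.
- Also as an improvement, report Table 5 abnormalities that were not present at baseline, on the model of the QTcF rows in Table 6.

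The cost is SAP wording and standard tables from data already collected. The downside is more output pages.

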**Table 5: Vital Sign Abnormality Definition**

Parameter	High Threshold	Low Threshold
Systolic blood pressure	$> 160 \text{ mmHg}$	$< 90 \text{ mmHg}$
Diastolic blood pressure	$> 100 \text{ mmHg}$	$< 60 \text{ mmHg}$
Heart rate	$> 100 \text{ bpm}$	$< 60 \text{ bpm}$
Temperature	$> 38^\circ\text{C}$	$< 35^\circ\text{C}$
Respiratory rate	$> 24/\text{min}$	$< 12/\text{min}$

### 7.6.5.2 Electrocardiogram

ECG (safety) parameters (numeric) will be summarized at baseline. Worst post-baseline and Worse post baseline change from baseline will also be summarized

Categorical outliers will be summarized in frequency tables. ECG finding at any timepoint will be determined as an outlier if the following criteria (which are assessed separately) are met for the ECG intervals (ie, QTcF, PR, QRS, HR).

**Table 6: ECG Outlier Criteria**

ECG Interval	Categorical Outlier Criteria
QTcF	Male: Treatment-emergent value of > 450 and $\leq$ 480 ms when not present at baseline (new onset)
	Male: Treatment-emergent value of > 480 and $\leq$ 500 ms when not present at baseline (new onset)
	Male: Treatment-emergent value of > 500 ms when not present at baseline (new onset)
	Increase of QTc from baseline of > 30 and $\leq$ 60 ms
	Increase of QTc from baseline > 60 ms
	Female: Treatment-emergent value of > 470 and $\leq$ 480 ms when not present at baseline (new onset)
	Female: Treatment-emergent value of > 480 and $\leq$ 500 ms when not present at baseline (new onset)
	Female: Treatment-emergent value of > 500 ms when not present at baseline (new onset)
	Increase of QTc from baseline of > 30 and $\leq$ 60 ms
	Increase of QTc from baseline > 60 ms
PR	Increase of PR from baseline > 25% resulting in PR > 200 ms
QRS	Increase of QRS from baseline > 25% resulting in QRS > 120 ms
HR	Decrease of HR from baseline > 25% resulting in HR < 50 bpm
	Increase of HR from baseline > 25% resulting in HR > 100 bpm

Number and percentages of categorical outliers will be summarized for each treatment group. A patient will be counted only once for a particular outlier event if the patient experiences more than 1 episode of that event.

#### **7.6.6 Listing of safety ECG Parameters will be Provided. COVID-19 Related Analyses**

A listing of patients who missed study visit(s) or study procedure(s) due to COVID-19 will be provided.

## 8.0 DATA MONITORING COMMITTEE AND SAFETY REVIEW

An SRC will be used for the dose escalation and dose expansion phases of the study. The SRC will be comprised of at least one site Investigator and the Sponsor's Medical Monitor. Additional participants may include representatives from the Sponsor's Clinical Development, Drug Safety, Biostatistics, and Clinical Pharmacology divisions as well as other functional representatives as needed to review safety data. For dose escalation cohorts, the SRC will jointly assess safety before opening dose escalation to each level. The exact dose will be confirmed based on review of safety data after a minimum of 3 patients have been enrolled in each level.

An independent, external, and multidisciplinary Data Safety Monitoring Committee (DSMC) composed of 3 to 5 members will be established and include at least 1 clinician knowledgeable in the field of the trial and at least 1 statistician. The DSMC will operate according to a prespecified charter and make recommendations on study conduct related to patient safety. The DSMC will review the progress of the study and perform reviews of safety data and provide recommendation to whether the nature, frequency, and severity of adverse effects associated with study treatment warrant the early termination of the study in the best interests of the participants, whether the study should continue as planned, or the study should continue with modifications.

CCI

# CCI

A large, bold, red logo consisting of the letters 'CCI' in a sans-serif font. The letters are slightly overlapping, with 'C' on the left, 'C' in the middle, and 'I' on the right. The logo is centered on a black rectangular background.

#### **9.1.4      Missing Data Imputation and Handling of Values Outside the Limits of Quantitation**

Missing values due to a missing sample or failed test will not be imputed. For cytokine assessment only, values reported as below the limit of quantitation (BLQ) at baseline, will be imputed as LLOQ (lower limit of quantitation). If LLOQ is not available, the minimum value across all samples will be used in place of the LLOQ to impute the values reported as BLQ. This imputation approach with LLOQ is only for baseline cytokine values, and not for post-baseline values.

Values reported as above the limit of quantitation (ALQ) post-baseline, will be imputed as ULOQ (upper limit of quantitation). If ULOQ is not available, the maximum value across all samples will be used in place of the ULOQ to impute the values reported as ALQ. The imputation approach is for post-baseline values only, and not for any baseline cytokine values.

## **10.0 PHARMACOKINETIC ANALYSIS**

### **10.1 Objectives of the Pharmacokinetic Analysis**

In addition to the objectives described in this section, PK data obtained in this study may also be combined with data from other studies to develop population PK models. These models may be used to evaluate the effects of intrinsic and extrinsic covariates on the PK of NKTR-255 and to determine measures of individual exposure for NKTR-255. Model predicted exposures may be used for exposure-response analyses of selected efficacy and safety endpoints. Population PK and/or exposure-response analyses will be specified in a separate analysis plan and the results will be reported separately.

CCI

### 10.3.2 Handling of Missing Values, BLQ Values, and Outliers

Missing concentration values will not be imputed. When summarizing concentrations, zero values will be excluded from the calculation of geometric means and CV% geometric mean, however, they will be included for all other summary statistics and the number of non-zero concentrations will be reported. Missing values for any PK parameters will not be imputed and will be handled as missing.

When calculating PK parameters, all Cycle 1 pre-dose concentrations that are below the limit of quantification (BLQ) will be set to 0; all other concentrations that are BLQ will be set to missing. Predose concentration for Cycle 2 and onward will be duplicated as D22 (504 hr, trough) for the previous cycle and predose on Day 1 for the scheduled cycle for the calculation of PK parameters. Concentration value of BLQ will be treated as missing for D22 (504 hr) of previous cycle and as 0 for the predose on Day 1 for the scheduled cycle.

CCI

CCI

CCI

CCI

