- a. All procedures and examinations should be performed before the administration of study drug(s) on dosing days, except as indicated. The acceptable visit window is + 1 day for Day 1. If scheduled visits or assessments coincide with a weekend or holiday, schedule at the next feasible date. Please contact the Medical Monitor to discuss any concerns about study visits or assessments that may fall out of the protocol-specified window because of unforeseen delays or other patient-specific circumstances. All out-of-window visits and procedures will incur a protocol deviation.
- b. The EOT visit should occur within 7 days after study treatment is discontinued, or before a new antineoplastic regimen has been initiated.
- c. Safety follow-up visit to occur 60 days after the last dose of study treatment. Survival follow-up visits will occur every 3 months from EOT.
- d. Includes previous immunotherapy, chemotherapy, targeted therapy, radiation therapy, prescription medications, over-the-counter medications, and herbal and dietary supplements.
- e. Patients with HNSCC must also have HPV and EBV status at Screening or provide historical assessment results.
- f. Brain MRI is only required for patients with a history of brain metastases. A standard-of-care brain MRI occurring prior to the 28-day screening window may be acceptable based on consultation with the Medical Monitor.
- g. See Section 7.13. Screening and End of Treatment physical examinations will be a complete physical examination. Symptom-directed physical examinations should be performed at the discretion of the Investigator to identify changes from baseline or to evaluate changes based on the patient's clinical symptoms during other clinic visits. The patient's height is measured at the Screening visit.
- h. The dose does not need to be recalculated for weight changes that are < 10% from baseline (Day -7).
- i. Vital signs to be recorded include temperature, pulse, respiration, systolic and diastolic blood pressure, and oxygen saturation (PaO2). PaO2 monitoring is required only at Screening and on dosing days. Collect vital signs before PK sample collection when both vital signs and PK samples are scheduled for the same timepoint, except EOI timepoint. CCI [REDACTED]  
[REDACTED]
- j. An echocardiogram or MUGA or nuclear scan for cardiac function and measurement of LVEF is required prior to dosing and may have been obtained within 60 days prior to C1D1.

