- k. On C1D1 and C2D1, ECGs are required predose and end of NKTR-255 infusion. All other timepoints, collect ECGs predose. Patients must be resting quietly in the supine position for  $\geq$  5 minutes prior to collection of 12-lead ECG.
- l. For women of childbearing potential (WCBP) only, perform a serum beta subunit of human chorionic gonadotropin ( $\beta$ -HCG) pregnancy test at Screening within 10 to 14 days prior to dosing, and urine or serum pregnancy test within 24 hours prior to day of dosing NKTR-255 on C1D1. In subsequent cycles, perform urine or serum test once each dosing cycle. A negative result is required prior to dosing. Pregnancy testing is not required for women who are postmenopausal for at least 1 year, or surgically sterile for at least 3 months prior to signing the ICF.

- m. See [Appendix 4](#). Central safety laboratory results must be used to determine patient eligibility, with the exception that pregnancy tests are done locally (see Section 7.11); thereafter, central laboratory samples must be obtained prior to each cycle. If local laboratory results are used for retreatment decisions due to timing issues (eg, predose, treatment-related AE management, dose delays, etc.), duplicate central safety laboratory tests must be submitted to the central laboratory.
- n. Tests include free or total triiodothyronine (T3) reflex testing if TSH is abnormal.
- o. Refer to the Laboratory Manual for sample processing. See [Table 7](#) for detailed sampling timepoints.

- u. NKTR-255 will be administered q21d starting C1D1.
- v. Cetuximab will be administered at the recommended dose according to the current local prescribing information, ie, IV weekly. A loading dose of 400 mg/m^2 IV is given as an initial dose, then weekly doses of 250 mg/m^2 IV. On days that NKTR-255 and cetuximab are both dosed, cetuximab should be administered first, [CCI](#)
- w. Patients will remain on treatment until meeting one of the criteria for discontinuation of treatment in Section [5.2.3.1](#).

CCI

CCI

CCJ

CCI

CCI

CCI

CCI

CCI

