### **5.2.4 Maintenance Period**

Patients in Phase 1b (dose escalation) **CCI** who achieve optimal response (PR or CR per RECIST 1.1) after at least 1 tumor assessment, as determined by the Investigator and in consultation with the Medical Monitor, will be given the option to continue treatment with NKTR-255 as single agent for maintenance q28d at the same dose as the patient's originally assigned dose.

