#### 5.3.1.6 Criteria to Resume NKTR-255

Patients will be permitted to resume study drug(s) at the same dose level(s) following resolution of the AE to Grade  $\leq 1$  or to baseline within 2 weeks after the completion of the prior cycle, with the exception of patients who meet criteria for permanent discontinuation as specified in Section 5.7.

Patients may resume treatment when the drug-related AE(s) resolve(s) to Grade  $\leq 1$  or baseline, with the following exceptions:

- Patients may resume treatment in the presence of Grade 2 fatigue.
- Patients with baseline Grade 1 AST/ALT or total bilirubin who require dose delays for reasons other than a 2-grade shift in AST/ALT or total bilirubin may resume treatment in the presence of Grade 2 AST/ALT **or** total bilirubin.
- Patients with combined Grade 2 AST/ALT **and** total bilirubin values meeting discontinuation parameters (see Section 5.7) should have treatment permanently discontinued.

A dosing delay lasting more than 2 weeks should be discussed with the Medical Monitor and the patient may resume the study if approved based on clinical assessment.

Tumor assessments should continue as per protocol even if dosing is delayed, and patients must otherwise meet the criteria for continued treatment at the time re-initiation of study therapy is considered.

If the decision is to resume study drug(s) dosing, the patient should restart treatment on the next regularly scheduled study drug(s) dosing visit. Skipped doses are not to be replaced.

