### 5.13.2 Pharmacokinetic Measurements

Blood samples for PK analyses will be collected from all patients (Section 1.2). Serial PK samples will be collected at multiple scheduled sampling times. Concentrations of NKTR-255 and cetuximab will be measured using validated method(s). Concentrations of additional analytes such as total PEG may also be analyzed in plasma samples. Pharmacokinetic parameters such as maximum peak concentration ( $C_{max}$ ), area under the concentration-time curve (AUC), CL, V, and  $t_{1/2}$  will be estimated from plasma concentration-time data where possible.

Blood samples for quantification of NKTR-255 and cetuximab concentrations will be drawn at times listed in the Schedule of Events (Section 1.2) CCI [REDACTED]. Blood samples for PK analysis will be processed as outlined in the Laboratory Manual. All on-treatment timepoints are intended to align with days on which study drug is administered. If a decision is made to delay dosing after collection of a predose sample, a second predose sample should not be collected. However, all postdose sampling should be adjusted accordingly. If it is known that a dose is going to be delayed, then the predose sample should be collected just prior to the delayed dose. Please refer to the Laboratory Manual for details.

CCI

CCI

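### SAP 10.3.2 files every later-cycle predose sample as the previous cycle's 504-hour trough, including samples the protocol has drawn later because the dose was delayed

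*SAP*

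**What the plan says.** SAP 10.3.2 gives each predose concentration from Cycle 2 on two roles. The first is as the last point of the cycle before: "Predose concentration for Cycle 2 and onward will be duplicated as D22 (504 hr, trough) for the previous cycle". The second is as the starting point of the new cycle: "predose on Day 1 for the scheduled cycle for the calculation of PK parameters". That wording places the copied value in the parameter calculation, so it is more than a table label. A BLQ result is handled separately: "Concentration value of BLQ will be treated as missing for D22 (504 hr) of previous cycle".

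The protocol sets the normal interval in the notes to Table 1: "NKTR-255 will be administered q21d starting C1D1", with "The acceptable visit window is + 1 day for Day 1". It also allows longer intervals:

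- Section 5.3.1.6 lets treatment resume up to 2 weeks after the prior cycle ends and leaves room for more: "A dosing delay lasting more than 2 weeks should be discussed with the Medical Monitor".
- Section 5.7 mentions delays of up to 6 weeks from the last dose, and longer ones with documented approval.
- Section 5.2.4 says Phase 1b responders "will be given the option to continue treatment with NKTR-255 as single agent for maintenance q28d".

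Section 5.13.2 decides when the sample is taken. If the delay is known beforehand, "the predose sample should be collected just prior to the delayed dose". If the delay is decided after the sample has been drawn, no second one is taken.

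**The concern.** The hour in the SAP rule is right only when the next NKTR-255 dose comes 21 days after the last. When a delay is known in advance, the protocol moves the sample with the dose, while the SAP still files it at 504 h of the cycle before. A concentration drawn one or more weeks late is then presented as the end-of-interval level of a 21-day cycle.

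Two outputs are exposed. The trough summary would contain values that are too low. Half-life, a planned parameter in Protocol 5.13.2, would be too short if the nominal hour is also used to fit the terminal slope. Protocol 5.3.1.5 ties NKTR-255 delays to drug-related toxicity, so affected values would tend to come from patients with toxicity. The documents give no data on how often delays occurred.

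**Working it through.** **The plan's own figure.** Day 22 begins (22 − 1) × 24 = 504 h after Day 1, and 21 × 24 = 504 h. The figure reproduces exactly for an on-time 21-day cycle.

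**Actual times the protocol allows**

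- +1 day window (Table 1 notes): 22 × 24 = 528 h
- 28-day maintenance, or a 7-day delay: 28 × 24 = 672 h
- 2-week delay after a completed cycle (Section 5.3.1.6): 35 × 24 = 840 h
- 6 weeks from last dose (Section 5.7): 42 × 24 = 1008 h

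**Effect on trough.** With log-linear decline and half-life h, the concentration at time T relative to that at 504 h is 2^(−(T − 504)/h). The documents give no half-life, so 24 to 168 h is an assumed range.

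| T (h) | h = 24 | h = 72 | h = 120 | h = 168 |
|---|---|---|---|---|
| 528 | 0.50 | 0.79 | 0.87 | 0.91 |
| 672 | 0.008 | 0.20 | 0.38 | 0.50 |
| 840 | <0.001 | 0.04 | 0.14 | 0.25 |
| 1008 | <0.001 | 0.008 | 0.05 | 0.125 |

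Example: T = 840, h = 168 gives 2^(−336/168) = 2^(−2) = 0.25.

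This error affects the tabulated trough whatever time is used for the slope. It needs a quantifiable value. The 504 h level relative to the initial level is 2^(−504/h): about 5 × 10⁻⁷ for h = 24, 0.8% for h = 72, 5% for h = 120 and 12.5% for h = 168. At the short end the sample is probably BLQ and is dropped. The longer half-lives are where the label can matter.

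**Effect on half-life, if nominal time enters the fit.** Take a previous quantifiable sample at s hours and a final sample drawn at T but entered at 504 h. The log-concentration drop is proportional to T − s, and it is divided by 504 − s. Hence apparent/true half-life = (504 − s)/(T − s), whatever the true half-life. The PK sampling table is redacted, so s = 336 h and s = 168 h are assumptions.

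| T (h) | s = 336 | s = 168 |
|---|---|---|
| 528 | 168/192 = 0.88 | 336/360 = 0.93 |
| 672 | 168/336 = 0.50 | 336/504 = 0.67 |
| 840 | 168/504 = 0.33 | 336/672 = 0.50 |
| 1008 | 168/672 = 0.25 | 336/840 = 0.40 |

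Regressions through more points fall within the same ranges. With earlier samples at 216 and 336 h the ratios are 0.62 (672 h) and 0.45 (840 h). With 168, 216 and 336 h they are 0.67 and 0.50. With actual times the ratio is 1.00 throughout.

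**The case against.** The best reply is that 504 h may be only a nominal label. Much of SAP Section 10 around 10.3.2 is redacted, as are the PK sampling details in the protocol. An actual-time rule, or one excluding out-of-window samples, could sit in the hidden text. That stands: it cannot be said that such a rule is missing or that half-life is in fact miscalculated. It does not rescue the trough label, because the readable sentence applies that label to every predose sample from Cycle 2 on.

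The scope is also narrower than it first appears:

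- A delay decided after the draw leaves the sample near 504 h.
- BLQ values are set to missing at Day 22, and the later the draw, the likelier a BLQ result. The largest ratios above are therefore the least likely to occur.
- Nothing visible shows PK sampling in 28-day maintenance cycles.

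All three limits stand.

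A reader might go further and infer that clearance and AUC are biased and that the RP2D choice was affected. The documents do not support this. Any bias in clearance or AUC depends on the same unseen choices and is not quantified here. PK is a stated input to the RP2D (Protocol 5.1.1), but no text says those decisions used parameters derived under this SAP sentence. The SAP itself covers a study in which only Phase 1b patients were enrolled (SAP 2.0).

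**Conclusion.** The point holds as a minor one. Read with Protocol 5.13.2, SAP 10.3.2 assigns a wrong hour and a wrong trough label to any predose sample drawn after a delay known in advance. The offset is 168 h for a 1-week delay and 336 h for a 2-week delay, and the reported trough is too low whenever the value is quantifiable.

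The half-life error is conditional. It needs the nominal hour in the terminal fit, a quantifiable value included in that fit, and log-linear decline. With a previous sample at 336 h or 168 h, half-life would then be 50-67% of the truth at 672 h and 33-50% at 840 h. For 28-day cycles, both errors arise only if PK is sampled in maintenance. On-time cycles, delays decided after the draw and BLQ values are not materially affected.

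**What to change.** State in SAP 10.3.2 that the duplicated predose sample enters parameter calculations at its actual elapsed time from the previous NKTR-255 infusion. State also that it is labelled or summarised as the 504 h trough only when the preceding interval was 21 days within the +1 day window. If redacted text already sets an actual-time rule, cross-reference it and add only the trough restriction.

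The cost is about one SAP sentence, since dosing and sampling times are needed for the PK analysis anyway. The downside is slightly fewer values in the 504 h trough summary. Samples up to 528 h would still carry the label, which leaves the small residual in the 528 h rows above for the trough; the parameter calculations would use actual time. No dosing or sampling procedure changes.
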